5.3. Medical History

Medical history collected at Screening in the core studies will be coded using the Medical Dictionary for Regulatory Activities (MedDRA) Version 21.0.

Medical history will be summarized by system organ class (SOC), preferred term (PT), treatment group, and overall. Subjects who report 2 or more medical history items that are coded to the same SOC and/or PT will be counted only once by the unique coded term in the summary. The summary will be provided for the Safety Analysis Set. No formal statistical testing is planned.

A by-subject listing of medical history will be provided by subject ID number.

6. EFFICACY ANALYSES

6.1. General Considerations

The primary analysis set for efficacy analyses will be the FAS, defined in Section 3.1.1.

If multiple valid, nonmissing efficacy measurements exist in an analysis window, records will be chosen based on the following rules if a single value is needed:

- The record closest to the nominal day for that visit will be selected
- If there are 2 records that are equidistant from the nominal day, or more than 1 record (with time known) on the selected day, the latest record will be taken
- If chronological order cannot be determined (eg, more than 1 record on the same day with time missing), for any given subject, the worst outcome will be selected.

For the calculation of composite endpoints including DAS28(CRP), ACR20/50/70, ACR-N, SDAI, CDAI and ACR/EULAR remission, we use the following steps unless otherwise specified:

- Step 1: Assign individual components to analysis visit windows defined in Section 3.5.2.
- Step 2: Within each analysis visit window, select the component-level data based on the rules for selecting efficacy data as above
- Step 3: Calculate the composite endpoint based on the selected component-level data in Step 2.

Below are the descriptions for the imputation methods that will be used throughout the efficacy analyses:

- Observed case (OC): Missing values remain missing. For the categorical composite endpoints, in the case that some components are missing, the composite endpoint assessment will be derived based on the non-missing components. If non-missing components are not sufficient to determine final composite endpoint, then the composite endpoint will be set as missing. For continuous composite endpoints (including ACR-N), if any components are missing, the composite endpoints will be set as missing.
- Non-responder imputation (NRI): For all binary response measurements, starting from OC, all missings will be set as non-responders.

If a subject only has core baseline measurements, OC analyses will not include this subject. But this subject will be treated as non-responder in NRI analyses.

For a specific visit if both regular CRP and high-sensitive CRP are available, only regular CRP will be used.

6.2. Efficacy Endpoints

The efficacy endpoints include:

- The proportion of subjects who achieve an American College of Rheumatology 20% improvement response (ACR20) over time
- The proportion of subjects who achieve an American College of Rheumatology 50% improvement response (ACR50) over time
- The proportion of subjects who achieve an American College of Rheumatology 70% improvement response (ACR70) over time
- Actual value and change from core baseline in individual components of the ACR response over time
- Actual value and change from core baseline in Disease Activity Score for 28 Joint Count using CRP (DAS28[CRP]) over time
- The proportion of subjects who achieve $DAS28(CRP) \leq 3.2$ over time
- The proportion of subjects who achieve $DAS28(CRP) < 2.6$ over time
- Actual value and change from core baseline in Clinical Disease Activity Index (CDAI) over time
- Actual value and change from core baseline in Simplified Disease Activity Index (SDAI) over time
- ACR-N over time
- European League Against Rheumatism (EULAR) response over time.
- The proportion of subjects who achieve ACR/EULAR remission over time
- Actual value and change from core baseline in SF-36 over time
- Actual value and change from core baseline in FACIT-Fatigue over time

6.3. Definition of Efficacy Endpoints

6.3.1. Tender/Swollen Joint Counts (TJC/SJC)

Tender joint count based on 68 joints (TJC68) and swollen joint count based on 66 joints (SJC66) will be collected during the course of the study. The assessment for each joint will be from the following selections: Tender Only, Swollen Only, Tender and Swollen, Joint Non-Evaluable or Missing, or Not Tender or Swollen.

Individual joint with missing assessment will not be imputed. If at least half of the joints are assessed at a given visit, the prorated tender and swollen joint counts will be calculated using the following formula:

$$TJC68 = \frac{\text{Total number of tender joints}}{68 - (\text{Number of nonevaluable or missing joints out of 68 joints})} \times 68$$

$$SJC66 = \frac{\text{Total number of swollen joints}}{66 - (\text{Number of nonevaluable or missing joints out of 66 joints})} \times 66$$

If less than half of joints are assessed at a given visit, joint counts are treated as missing for that visit.

A more abbreviated assessment considering 28 joints as listed in [Table 6-1](#) for both tenderness and swelling will also be conducted (as part of the TJC68 and SJC66 assessment), denoted as TJC28 and SJC28, respectively.

Table 6-1. Composition of the 28 Joints

Joints	Number
Shoulder Joints (Left and Right)	2
Elbow Joints (Left and Right)	2
Wrist Joints (Left and Right)	2
Metacarpophalangeal Joints I-V (Left and Right)	10
Hand Proximal Interphalangeal Joints I-V (Left and Right)	10
Knee Joints (Left and Right)	2

If there exist non-evaluable or missing joints among the 28 joints, similar prorated tender and swollen joint counts will be calculated as follows:

$$TJC28 = \frac{\text{Total number of tender joints}}{28 - (\text{Number of nonevaluable or missing joints out of 28 joints})} \times 28$$

$$SJC28 = \frac{\text{Total number of swollen joints}}{28 - (\text{Number of nonevaluable or missing joints out of 28 joints})} \times 28$$

If less than half of the 28 joints are assessed at a given visit, TJC28 and SJC28 are treated as missing for that visit.

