- Increases in dosage or dosing regimen of, or initiation of, potent P-gp inducers (e.g. rifampin, phenytoin, carbamazepine, and St. John's wort). Subjects already on stable doses should continue per investigator judgment.

Subjects may receive a maximum of 3 intra-articular injections of corticosteroid every 12 months while participating in this open-label extension study. The dose of corticosteroid injected should not exceed the anti-inflammatory equivalent dose of prednisone 40 mg suspension. The dose and volume should be adjusted downward as appropriate to the size of the joint. For the analysis of the TJC68 and SJC66, these joints will be considered "not assessable" for 3 months from the time of the intra-articular injection.

Vaccine Guidelines:

- Prior to study participation, it is recommended that the subject's vaccinations be brought up to date according to local vaccination standards.
- Live or attenuated vaccines (including, but not limited to varicella and inhaled flu vaccine) are prohibited within 30 days of Day 1, throughout the study, and for 6 weeks after the last dose of study drug.
- Subjects should be advised to avoid routine household contact with persons vaccinated with live/attenuated vaccine components. General guidelines suggest that a study subject's exposure to household contacts should be avoided for the below stated time periods:

- Varicella or attenuated typhoid fever vaccination – avoid contact for 4 weeks following vaccination
- Oral polio vaccination -- avoid contact for 6 weeks following vaccination
- Attenuated rotavirus vaccine -- avoid contact for 10 days following vaccination
- Inhaled flu vaccine -- avoid contact for 1 week following vaccination

Inactivated vaccines (such as inactivated flu vaccines) should be administered according to local vaccination standards whenever medically appropriate; however, there are no available data on the concurrent use of filgotinib and its impact on immune responses following vaccination.

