8.8.1 Efficacy and Safety Measurements Assessed and Flow Chart

8.8.1.1 Efficacy Assessments

8.8.1.1.1 Evaluation of Disease Activity

Efficacy assessments (excluding FACIT and SF-36) will be carried out at every visit, except the Follow-up Visit. FACIT and SF-36 will be carried out at the AV and the Final Visit/EDV.

Each of 68 joints will be evaluated for tenderness, and each of 66 joints will be evaluated for swelling, except upon receipt of an intra-articular injection of corticosteroid in the previous 3 months, where joints will be classed as not assessable (Appendix 13.2).

A joint assessor with adequate training and experience in performing joint assessments will be designated at each study site to perform all joint assessments. The joint assessor should preferably be a rheumatologist; however, if a rheumatologist is not available, it should be a health care worker with at least one year's experience in performing joint assessments. The assessor should remain the same throughout the study per subject, as much as possible. It is required that the designated joint assessor identify an appropriate back up assessor to provide coverage if the designated joint assessor is absent.

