8.9.1.4 Efficacy Variables

The efficacy analysis may combine the data of all 3 studies (GLPG0634-CL-203, GLPG0634-CL-204, and GLPG0634-CL-205).

Definition of Efficacy Endpoints

ACR20

The ACR response is a measurement of improvement in multiple disease assessment criteria. The ACR20 response is defined as:

≥20% improvement from Baseline in SJC66 and TJC68

AND

≥20% improvement from Baseline in at least 3 of the following 5 assessments:

- Pain (VAS) in cm (from HAQ-DI).
- Patient's Global Assessment of Disease Activity (VAS) in cm.
- Physician's Global Assessment of Disease Activity (VAS) in cm.
- Patient's Assessment of Physical Function as measured by HAQ-DI.
- CRP in mg/dL or mg/L.

ACR50 and ACR70

ACR50 and ACR70 are similarly defined as ACR20, except the improvement threshold from Baseline is 50% and 70%, respectively.

ACR-N

The ACR-N⁷ is the smallest percentage improvement in swollen and tender joints and the median of the remaining 5 core parameters, and is expected to be more sensitive to change than the ACR20, ACR50, or ACR70.

ACR-N = MIN [%improvement in TJC68,

%improvement in SJC66,

MED %improvement in (Patient's Global Assessment, Physician's

Global Assessment, patient's assessment of pain, HAQ-DI, CRP)]

ACR/EULAR Remission

A subject's disease activity status can be defined as being in remission:

when scores on the TJC28, SJC28, CRP (actual value in mg/dL), and Patient Global Assessment of Disease Activity (cm) are all ≤ 1 .

Simplified Disease Activity Index (SDAI)

The SDAI⁹ is the numerical sum of 5 outcome parameters: TJC28, SJC28, Patient's Global Assessment of Disease Activity (in cm), Physician's Global Assessment of Disease Activity (in cm), and CRP (mg/dL).

$SDAI = TJC28 + SJC28 + \text{Patient's Global Assessment of Disease Activity (VAS in cm)} + \text{Physician's Global Assessment of Disease Activity (VAS in cm)} + CRP \text{ (mg/dL)}$

The SDAI can be categorized:

- High disease activity: $SDAI > 26$
- Moderate disease activity: $[11, 26]$
- Low disease activity: $[3.3, 11]$
- Remission: ≤ 3.3

Clinical Disease Activity Index (CDAI)

The CDAI⁹ is the SDAI modified to exclude CRP.

$CDAI = TJC28 + SJC28 + \text{Patient's Global Assessment of Disease Activity (VAS in cm)} + \text{Physician's Global Assessment of Disease Activity (VAS in cm)}$

The CDAI can also be categorized:

- High disease activity: > 22
- Moderate disease activity: $[10, 22]$
- Mild disease activity: $[2.8, 10]$
- Remission: ≤ 2.8

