6.3.10. ACR/EULAR remission

ACR/EULAR remission is achieved when $TJC28 \leq 1$ and $SJC28 \leq 1$ and $CRP \leq 1$ mg/dL and $SGA \leq 1$ (on a 0-10 cm scale). ACR/EULAR remission is not achieved when at least 1 of the 4 components has a value > 1.

In case that some components are missing, ACR/EULAR remission is not achieved if at least 1 of the non-missing components has a value > 1. If non-missing components are not sufficient to determine ACR/EULAR remission, then ACR/EULAR remission will be considered as missing.

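### The ACR/EULAR remission cut-off of at most 1 joint is applied to a non-integer prorated count, so one active joint plus any unassessed joint among the 28 is coded as definite non-remission

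*SAP*

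**What the plan says.** **Proration.** SAP 6.3.1 provides: "If there exist non-evaluable or missing joints among the 28 joints, similar prorated tender and swollen joint counts will be calculated as follows". The divisor is 28 less the "Number of nonevaluable or missing joints out of 28 joints". The lower limit is: "If less than half of the 28 joints are assessed at a given visit, TJC28 and SJC28 are treated as missing for that visit". Proration therefore covers 1 to 14 unassessed joints.

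**Remission rule.** SAP 6.3.10 requires TJC28, SJC28, CRP (mg/dL) and the subject's global assessment (cm) each to be at most 1, and adds: "ACR/EULAR remission is not achieved when at least 1 of the 4 components has a value > 1". Protocol 8.9.1.4 has the same cut-off, "when scores on the TJC28, SJC28, CRP (actual value in mg/dL), and Patient Global Assessment of Disease Activity (cm) are all" at most 1, and does not mention proration.

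**Link between the two.** The last step for composites in SAP 6.1 is: "Calculate the composite endpoint based on the selected component-level data in Step 2". No section rounds the prorated count, returns to the raw count for remission, or exempts remission from proration.

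**Where unassessed joints come from.** Protocol 8.8.1.1.1 describes joints with a recent corticosteroid injection, "where joints will be classed as not assessable". Protocol 8.6.8 makes this last "for 3 months from the time of the intra-articular injection" and allows up to three injections in 12 months. Section 8.6.8 speaks of the 68- and 66-joint counts, but SAP 6.3.1 takes the 28-joint counts from that same assessment. Its joint-level response options also include a non-evaluable or missing category.

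**The concern.** A joint count is an integer, and a cut-off of at most 1 is meant to separate 0 or 1 active joints from 2 or more. Proration replaces the count with an estimate that need not be an integer. Once any of the 28 joints is unassessed, one active joint always gives an estimate above 1, by as little as 0.04, and the SAP reads that excess as proof of failure.

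The result is coded as observed, not as missing. It therefore enters the OC summary as a non-remission, and the NRI summary too. This sits badly with the principle in SAP 6.1 and 6.3.10 that a composite is left missing when the available information cannot settle it.

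The situation is foreseeable. Visits fall every 12 weeks (protocol 8.7.2.1) and an injected joint is out for 3 months, so one injection will normally touch at least one efficacy visit. ACR/EULAR remission is a protocol secondary endpoint and is tabulated over time (SAP 6.2).

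**Working it through.** The documents give no figure of their own to reproduce here. The check evaluates the SAP 6.3.1 formula against the SAP 6.3.10 cut-off.

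**Inputs.** 28 joints (SAP Table 6-1: 2 + 2 + 2 + 10 + 10 + 2 = 28). Let *k* be the number of active joints among those assessed and *m* the number unassessed, with *m* = 1 to 14 for proration. The cut-off is at most 1.

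**Formula.** Prorated count = 28*k* / (28 − *m*).

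| *m* | *k* = 0 | *k* = 1 | SAP result for *k* = 1 | *k* = 1, rounded |
|---|---|---|---|---|
| 0 | 0 | 1.000 | met | 1 |
| 1 | 0 | 28/27 = 1.037 | failed | 1 |
| 2 | 0 | 28/26 = 1.077 | failed | 1 |
| 4 | 0 | 28/24 = 1.167 | failed | 1 |
| 7 | 0 | 28/21 = 1.333 | failed | 1 |
| 9 | 0 | 28/19 = 1.474 | failed | 1 |
| 10 | 0 | 28/18 = 1.556 | failed | 2 |
| 14 | 0 | 28/14 = 2.000 | failed | 2 |

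With *k* = 1, every *m* from 1 to 14 fails. With *k* = 0, every *m* up to 14 passes. So zero active joints with 14 unassessed can be remission, while one active joint with one unassessed cannot.

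**Direction of error when exactly one joint is unassessed.**
- *k* = 0: the true count is 0 or 1. Coded as met, which is always right.
- *k* of 2 or more: the true count is above 1. Coded as failed, which is always right.
- *k* = 1: the true count is 1 or 2. Coded as failed, which is right only if the unassessed joint is active. Proration itself assumes the rate seen in the assessed joints, 1/27. At that rate the criterion is truly met with probability 1 − 1/27 = 96.3%.

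**Direction when two or more are unassessed.** With *k* = 0 the joint criterion is coded as met, yet the true count could be 2 or more. That error favours remission, so the two effects oppose each other.

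**Effect on the other scores.** For *k* = 1 and *m* = 1, DAS28(CRP) rises by 0.56 × (√(28/27) − 1) = 0.010 if the joint is tender only, and by 0.84 × (√(28/27) − 1) = 0.015 if it is tender and swollen. The difficulty belongs to the hard cut-off, not to proration in general.

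**The case against.** The best case for leaving the text alone has four parts.

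- **Remission is not proven for these subjects.** The true count is 1 or 2, and a recently injected joint is unlikely to be missing at random. In an open-label study, erring against remission is a defensible choice. This stands in part. However, the SAP does not present its rule as a conservative choice, and for *m* = 1 the failure code is the likelier truth only if the unassessed joint has more than an even chance of being active.
- **An undetermined status would leave NRI unchanged.** If one active and one unassessed joint were treated as unresolved, SAP 6.1 would make it missing under OC and a non-responder under NRI. That is correct. The NRI result changes only under a rule that lets the subject pass, as rounding does.
- **The overall direction is unknown.** A reader might infer that the trial's remission rate is biased downwards. The documents do not support that: passing zero active joints with several unassessed works the other way.
- **The reach is narrow.** A reader might infer that anyone with one active and one unassessed joint loses remission. In fact both joints must be among the 28 in Table 6-1; an unassessed joint elsewhere leaves the 28-joint count at exactly 1. CRP, the global assessment and the other joint count must also qualify already.

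**Conclusion.** Wrong as written, and minor. Read literally, SAP 6.3.1 and 6.3.10 together turn at most one active joint into no active joint for a subject who has 1 to 14 of the 28 joints unassessed and otherwise meets every remission criterion. The classification is a definite failure in both OC and NRI.

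With one unassessed joint, misclassification on the joint criterion can only go against remission. The 96.3% figure rests on proration's own assumption that the unassessed joint behaves like the assessed ones. With several unassessed joints the net direction is not established.

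The number of subjects affected cannot be computed, because the documents give no rate of unassessed joints, of one-joint status or of remission. For scale only, suppose 5% to 10% of otherwise qualifying subjects have an unassessed joint among the 28, and 30% to 40% of them have a count of exactly 1. Then 0.05 × 0.30 = 1.5% to 0.10 × 0.40 = 4% of remissions would be lost, and an assumed rate of 25% would read 24.6% to 24.0%. All these inputs are assumptions, and the sum ignores the opposing error. The effect is probably small, and SAP 6.4 plans description only, with no formal test.

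**What to change.** Add one sentence to SAP 6.3.10: when at least half of the 28 joints are assessed, the cut-off of 1 is applied to the prorated TJC28 and SJC28 after rounding to the nearest integer. Keep unrounded prorated counts for DAS28(CRP), SDAI, CDAI and the ACR measures.

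One active joint then passes with 1 to 9 unassessed joints and fails with 10 to 14. No tie arises, since 28/(28 − *m*) is never exactly 1.5 for a whole number *m*. Results for zero active joints, and for two or more, do not change.

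A single rule has to be chosen. Applying the cut-off to the raw count of active joints agrees with rounding up to 9 unassessed joints but also passes one active joint with 10 to 14 unassessed.

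The cost is one sentence and one line of programming. The downside is that a few subjects whose unassessed joint is truly active would be counted as in remission. At proration's own rate, and treating joints as independent, the chance that a pass on one active joint is wrong is 1/27 = 3.7% with one joint unassessed. It rises to 1 − (18/19)^9 = 38.5% with nine.

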6.3.2. Global Assessment of Disease Activity

Subject's Global Assessment of Disease Activity (SGA) and Physician's Global Assessment of Disease Activity (PGA) based on a 0-100 mm visual analog scale (VAS) will be recorded during the study, with 0 indicating "no disease activity" and 100 indicating "maximum disease activity" (or similar description of disease severity).

6.3.3. Health Assessment Questionnaire Disability Index (HAQ-DI)

The HAQ-DI score is defined as the average of the scores of eight functional categories (dressing and grooming, arising, eating, walking, hygiene, reach, grip, and other activities), reported by the patient. Responses in each functional category are collected as: without any difficulty; with some difficulty; with much difficulty; unable to do a task in that area and with or without aids or devices. The HAQ-DI score ranges from 0 (no disability) to 3 (completely disabled), when 6 or more categories are non-missing. Detailed algorithm for calculating HAQ-DI score is described in [Appendix 2](#).

HAQ-DI also includes a separate pain assessment and subject will be requested to mark the severity of the pain in the past week on a 0-100 mm VAS, with 0 indicating "no pain" and 100 indicating "severe pain".

6.3.4. ACR20

A subject achieves ACR20 response when this subject has

- $\geq 20\%$ improvement from core baseline in TJC68, AND
- $\geq 20\%$ improvement from core baseline in SJC66, AND
- $\geq 20\%$ improvement from core baseline in at least 3 of the following 5 items:
 - 1) PGA
 - 2) SGA
 - 3) Subject's pain assessment
 - 4) HAQ-DI score
 - 5) CRP

Percent improvement from core baseline at a postbaseline visit is calculated as follows for all 7 components mentioned above:

$$\% \text{ improvement} = \frac{\text{baseline value} - \text{postbaseline value}}{\text{baseline value}} \times 100$$

If the core baseline value is 0 then the percent improvement from core baseline is set to missing.

In the case that some ACR20 components are missing, the ACR20 assessment will be based on the non-missing components. If non-missing components are not sufficient to determine ACR20 response, then the ACR20 response will be considered as missing.

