6.3.5. ACR50 and ACR70

ACR50 and ACR70 are similarly defined as ACR20 (see Section 6.3.4.), except the improvement threshold from core baseline is 50% and 70%, respectively

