6.3.8. ACR-N

ACR-N is defined as the smallest percentage improvement from core baseline in swollen joints, tender joints and the median of the following 5 items (PGA, SGA, Patient pain assessment, HAQ-DI score and CRP). It has a range between 0 and 100%. In particular,

ACR-N = min {improvement in TJC68 (%), improvement in SJC66 (%), median [improvement in SGA (%), improvement in PGA (%), improvement in pain assessment (%), improvement in HAQ-DI (%), improvement in CRP (%)]}.

If this calculation results in a negative value, then the ACR-N is set to 0. If any components are missing, the ACR-N will be set as missing.

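### A core baseline of 0 is coded as missing rather than not improved, so some certain ACR20/50/70 non-responders leave the observed-case rate and the subject has no ACR-N at any visit

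*SAP*

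**What the plan says.** SAP 6.3.4 gives one percent-improvement formula: "Percent improvement from core baseline at a postbaseline visit is calculated as follows for all 7 components mentioned above". It then adds: "If the core baseline value is 0 then the percent improvement from core baseline is set to missing". Beyond the two joint-count criteria, ACR20 needs the required "improvement from core baseline in at least 3 of the following 5 items". On incomplete data the section says: "If non-missing components are not sufficient to determine ACR20 response, then the ACR20 response will be considered as missing". SAP 6.3.5 carries the scheme to the higher thresholds: "ACR50 and ACR70 are similarly defined as ACR20".

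For ACR-N, SAP 6.3.8 says: "If any components are missing, the ACR-N will be set as missing". SAP 6.1 says the same in general: "For continuous composite endpoints (including ACR-N), if any components are missing, the composite endpoints will be set as missing".

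SAP 6.1 also defines NRI: "For all binary response measurements, starting from OC, all missings will be set as non-responders". Under SAP 6.4, binary endpoints are summarised both as OC and with NRI, and continuous endpoints as OC only. The endpoint definitions in protocol 8.9.1.4 contain no rule for a zero baseline.

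**The concern.** HAQ-DI and the pain, patient global and physician global scales all have 0 as their best value. An item at 0 at core baseline cannot improve by 20%, 50% or 70%, so nothing about it is unknown. The SAP nevertheless gives it the status of an unobserved value. Because the core baseline is fixed, that status holds at every visit.

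Two summaries are exposed. In the OC analysis of ACR20/50/70, a subject who cannot be a responder may be called undetermined and dropped from the denominator. In ACR-N, the subject is lost for the whole study although the value could be worked out.

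**Working it through.** The plan gives no figure for this point, so there is none to reproduce. The check has three parts.

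**1. Which response patterns change.** Inputs are the SAP 6.3.4 rules. Each component is improved, not improved or missing. The three-of-five condition is met if at least 3 items improved, fails if improved plus missing items number fewer than 3, and is otherwise undetermined. A failed joint criterion gives non-response regardless. I compared coding a zero-baseline item as missing (SAP) with coding it as not improved.

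Both joint criteria met:

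| Zero-baseline items among the 5 | Other items improved | SAP result | Result if counted as not improved |
|---|---|---|---|
| 1 | 0 or 1 of 4 | non-response | non-response |
| 1 | 2 of 4 | missing | non-response |
| 1 | 3 or 4 of 4 | response | response |
| 2 | 0 of 3 | non-response | non-response |
| 2 | 1 or 2 of 3 | missing | non-response |
| 2 | 3 of 3 | response | response |
| 3 | any | missing | non-response |

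With one zero-baseline item there are 4 × 16 = 64 patterns over the two joint criteria and the other four items: 5 are responses and 53 non-responses under both codings, and 6 go from missing to non-response. No pattern goes from missing to response, so the effect has one direction. A zero joint count would behave the same way (16 of 64 patterns missing, all of them certain non-responses).

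**2. A constructed subject.** HAQ-DI is 0 at core baseline and stays 0. TJC68 goes from 20 to 8 and SJC66 from 15 to 6 (60% each). Both globals go from 60 to 30 (50% each). Pain and CRP do not change (0%).

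- ACR20 and ACR50: 2 items improved, 1 missing, and 2 + 1 = 3, so the SAP result is missing. At most 2 of 5 can improve, so the true result is non-response.
- ACR70: the joint counts fail at 60%, so non-response either way.
- If pain also falls from 60 to 30, three items reach 50% and the subject is an ACR20 and ACR50 responder. ACR-N is still missing under the SAP. Ranking HAQ-DI as 0%, the items are 50, 50, 50, 0, 0 with median 50, and ACR-N = min(60, 60, 50) = 50.

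The choice of 0% does no harm if the item has in fact worsened. If at least three other items improved, the median is one of those and does not depend on the zero-baseline item. Otherwise the median is 0 or less, and SAP 6.3.8 sets a negative ACR-N to 0 anyway.

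**3. Size.** Let R be the true response rate among subjects otherwise evaluable at a visit, f the share with a zero-baseline item, and q the share of those in an undetermined pattern. Then

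OC rate = R / (1 − f·q), and shift = R / (1 − f·q) − R.

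N = 739 (protocol 8.3.1). The values of f, q and R are **assumed**.

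| f | q | Subjects dropped from OC (739·f·q) | Shift at R = 50% | Subjects without ACR-N (739·f) |
|---|---|---|---|---|
| 1% | 5% | 0.4 | 0.50/0.9995 − 0.50 = +0.03 points | 7 |
| 5% | 10% | 3.7 | 0.50/0.995 − 0.50 = +0.25 points | 37 |
| 10% | 20% | 14.8 | 0.50/0.98 − 0.50 = +1.02 points | 74 |

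At R = 80% the last row gives 0.80/0.98 − 0.80 = +1.63 points. There q = 20% is already the ceiling if zero-baseline subjects respond at 80%, since q cannot exceed their non-response rate.

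**The case against.** **NRI is right.** Every affected subject is a true non-responder, and NRI makes them one. The NRI table stands beside the OC table for each binary endpoint. This stands: a reader might infer that the ACR response results as a whole are inflated, and SAP 6.1 and 6.4 do not support that. The OC table remains affected. In an open-label period of approximately 96 months NRI also counts every dropout as a non-responder, so OC will be read as well. NRI does nothing for ACR-N.

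**Zero baselines may be rare.** CL-203 enrolled subjects with active RA, so zero joint counts look unlikely. SAP 3.4 replaces CRP below the quantitation limit by a value above 0. That rule is written for descriptive statistics, and I take it to hold for the composites too. HAQ-DI of 0 is the most plausible source. This stands, and it keeps the point minor.

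**The wording could be read otherwise.** SAP 6.3.4 makes the percent improvement missing, whereas 6.3.8 speaks of components, and the raw component is observed. The ACR-N formula is built from percent improvements, so missing is the natural reading. If two programmers could differ, the text still needs a sentence.

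**The two composites differ by design.** A reader might infer that the SAP contradicts itself by scoring a subject on ACR20 but not on ACR-N. It does not: SAP 6.1 deliberately sets separate missing-component rules for categorical and continuous composites. The fault lies in calling a known quantity missing.

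**Little depends on it.** Efficacy is a secondary objective, and the analysis is descriptive without testing. That is fair.

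**Conclusion.** The point holds as a minor correction. A zero core baseline turns some certain ACR20/50/70 non-responses into missing values, and the OC rate can only be biased upward as a result. It also removes the subject from ACR-N at all visits, with no second analysis to recover the value.

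The direction follows from the SAP text alone. The size does not: with f between 1 and 10% and q between 5 and 20%, the OC shift is about +0.03 to +1.0 points at a 50% response rate, and about 7 to 74 of 739 subjects lose ACR-N. Neither share is in the documents.

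A reader might also infer that ACR-N ends up describing a different, more disabled population. The documents do not support that. The share lost is unknown, and only a zero HAQ-DI concerns disability; a zero on pain or a global scale does not.

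**What to change.** - **SAP 6.3.4 and 6.3.5:** state that any of the five items with a core baseline of 0 counts as not improved at every post-baseline visit.
- **SAP 6.3.8:** state that a zero-baseline item is ranked as no improvement (0%) in the median of five and does not make ACR-N missing.
- Leave the handling of truly missing components in 6.1 and 6.3.8 unchanged.

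Taking the median over the available items would be the wrong repair. In the constructed subject the four remaining items are 50, 50, 0, 0, with median 25, so a certain ACR20 non-responder would receive ACR-N = min(60, 60, 25) = 25. Ranked over five items, the median and ACR-N are 0.

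The cost is a sentence in each place and a small derivation change, with no new data. OC rates become slightly less favourable; NRI rates do not change. Reporting the number of subjects with a zero core baseline, by item, would replace the assumed range with a count.
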